5.1 Statistical Methods

5.1.1 Hypotheses and Statistical Methods for Primary Objectives

5.1.1.1 Hypotheses

STAGE I:

Individual Hypotheses for Each Serotype:

A non-inferiority testing approach will be performed for each serotype to show the non-inferiority of 2 doses of CYD dengue vaccine (28 days after last vaccination) compared to the 3 dose of CYD dengue vaccine, in subjects seropositive at baseline.

The non-inferiority testing approach will also be performed for each serotype to show the non-inferiority of 2 doses of CYD dengue vaccine (1 year after last injection) compared to the 3 doses of CYD dengue vaccine, in subjects seropositive at baseline.

Individual hypotheses for each serotype will be as follows:

$$H_0^{ij}: GMT_{Group\ j}^i / GMT_{Group\ 1}^i \leq \frac{1}{\delta}$$

$$H_1^{ij}: GMT_{Group\ j}^i / GMT_{Group\ 1}^i > \frac{1}{\delta}$$

Where:

i=1, 2, 3, and 4 (each serotype),

j=2

δ the non-inferiority margin, is set to 2, i.e. 0.301 (=log10 [2]).

The overall non-inferiority of Group 2 to Group 1 at 28 days after last injection will be demonstrated if all 4 individual serotype null hypotheses are rejected. The same, overall non-inferiority of Group 2 to Group 1 at 1 year after last injection will be demonstrated if all 4 individual serotype null hypotheses are rejected.

STAGE II:

The non-inferiority testing for within Group 1 comparisons will be performed in STAGE II regardless of whether non-inferiority is achieved or not for either test in STAGE I. However, only Group 1 and Group 2 that achieve non-inferiority at 28 days after last vaccination in STAGE I will continue to be tested in STAGE II for the between Group 1 comparisons.

Individual Hypotheses for Each Serotype:

Paired Test (Within Group 1)

A non-inferiority testing approach will be performed for each serotype to show the non-inferiority of a CYD booster dose (28 days after booster) either 1 year and/or 2 years after last vaccination compared to the third CYD dose (28 days after third vaccination), i.e., within Group 1 comparisons, in subjects seropositive at baseline. A Bonferonni alpha adjustment will be used to control for multiplicity.

Individual hypotheses for each serotype will be as follows:

$$H_0^{ij}: GM(V_{Booster\ j}^i / V_{PD3\ j}^i) \leq \frac{1}{\delta}$$

$$H_0^{ij}: GM(V_{Booster\ j}^i / V_{PD3\ j}^i) > \frac{1}{\delta}$$

Where:

i=1, 2, 3, and 4 (each serotype),

j=1a or 1b (subgroup)

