5.1.1.2 Statistical Methods

STAGE I:

The non-inferiority tests will be performed using the two sample t-test 95% 2 sided CI of the difference of the means of the log₁₀ transformed post-vaccination titer between Group 2 and Group 1 ($\alpha=2.5\%$ one sided) at 28 days and 1 year after last injection. For each serotype, non-inferiority will be demonstrated if the lower limit of the two sided adjusted 95% CI is greater than 1/2 (i.e., the log 10 of the difference should be above -0.301).

STAGE II:

Paired Test (Within Group 1)

The non-inferiority tests will be performed using the paired t-test adjusted 95% 2 sided CI ($100*[1 - \alpha/\text{total number of overall hypothesis tests to perform in STAGE II}]$ CI [Bonferonni adjustment to control for multiplicity]) of the difference of the means of the log₁₀ transformed post-vaccination titer between booster j and post Dose 3 j ($\alpha=2.5\%$ one sided). For each serotype, non-inferiority will be demonstrated if the lower limit of the 2-sided adjusted 95% CI is greater than 1/2 (i.e., the log 10 of the difference should be above -0.301). Subjects with non-missing post dose 3 and post booster titer will be included in this analysis.

Two Sample Test (Between Group 1 and Group 2)

The non-inferiority tests will be performed using the two sample t-test adjusted 95% 2 sided CI ($100*[1 - \alpha/\text{total number of overall hypothesis tests to perform in STAGE II}]$ CI [Bonferonni adjustment to control for multiplicity]) of the difference of the means of the log₁₀ transformed post-vaccination titer between Group j and Group 1 ($\alpha=2.5\%$ one sided). For each serotype, non-inferiority will be demonstrated if the lower limit of the two sided adjusted 95% CI is greater than 1/2 (i.e., the log 10 of the difference should be above -0.301).

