5.1.2 Hypotheses and Statistical Methods for Secondary Objectives

5.1.2.1 Hypotheses

If the hypothesis for non-inferiority is demonstrated for the primary objective, then superiority hypotheses will be performed.

STAGE I

Individual Hypotheses for Each Serotype:

A superiority testing approach will be performed for each serotype to show the superiority of 2 doses of CYD dengue vaccine (28 days after last injection) compared to 3 doses of CYD dengue vaccine, in subjects seropositive at baseline. A superiority testing approach will also be performed for each serotype to show the superiority of 2 doses of CYD dengue vaccine (1 year after last injection) compared to the 3 doses of CYD dengue vaccine, in subjects seropositive at baseline.

A Bonferonni alpha adjustment will be used to control for multiplicity.

Individual hypotheses for each serotype will be as follows:

$$H_0^{ij}: GMT_{Group\ j}^i / GMT_{Group\ 1}^i \leq 1$$

$$H_1^{ij}: GMT_{Group\ j}^i / GMT_{Group\ 1}^i > 1$$

Where:

i=1, 2, 3, and 4 (each serotype),

j=2

The overall superiority of Group 2 to Group 1 at 28 days after last injection will be demonstrated if all 4 individual serotype null hypotheses are rejected. The same, overall superiority of Group 2 to Group 1 at 1 year after last injection will be demonstrated if all 4 individual serotype null hypotheses are rejected.

STAGE II:

Individual Hypotheses for Each Serotype:

Paired Test (Within Group 1)

A superiority testing approach will be performed for each serotype to show the superiority of a CYD dengue vaccine booster dose (28 days after booster) either 1 year and/or 2 years after last injection compared to the third CYD dose (28 days after third vaccination), i.e., within Group 1 comparisons, in subjects seropositive at baseline. A Bonferonni alpha adjustment will be used to control for multiplicity.

Individual hypotheses for each serotype will be as follows:

$$H_0^{ij}: GM(V_{Booster\ j}^i / V_{PD3\ j}^i) \leq 1$$

$$H_1^{ij}: GM(V_{Booster\ j}^i / V_{PD3\ j}^i) > 1$$

Where:

i=1, 2, 3, and 4 (each serotype),

j=1a or 1b (sub-group)

The overall superiority of Group j (j=1a or 1b) at 28 days after booster injection to Group j (j=1a or 1b) at 28 days after last 3rd-injection will be demonstrated if all 4 individual serotype null hypotheses are rejected.

Two Sample Test (Between Group 1 and Group 2)

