5.1.2.2 Statistical Methods

5.1.2.2.1 Statistical Methods for Hypotheses Objectives

STAGE I:

The superiority tests will be performed using the two sample t-test 95% 2 sided CI of the difference of the means of the log10 transformed post-vaccination titer between Group 2 and Group 1 ($\alpha=2.5\%$ one sided) at 28 days and 1 year after last injection. For each serotype, superiority will be demonstrated if the lower limit of the two sided adjusted 95% CI is greater than 1 (i.e., the log 10 of the difference should be above 0).

STAGE II:

Paired Test (Within Group 1)

The superiority tests will be performed using the paired t-test adjusted 95% 2 sided CI ($100*[1-\alpha/\text{total number of overall hypothesis tests for non-inferiority to perform in STAGE II}]$ CI [Bonferonni adjustment to control for multiplicity]) of the difference of the means of the log10 transformed post-vaccination titer between booster j and post Dose 3 j ($\alpha=2.5\%$ one sided). For each serotype, superiority will be demonstrated if the lower limit of the two sided adjusted 95% CI is greater than 1 (i.e., the log 10 of the difference should be above 0). Subjects with non-missing post dose 3 and post-booster titer will be included in this analysis.

Two Sample Test (Between Group 1)

The superiority tests will be performed using the two sample t-test adjusted 95% 2 sided CI ($100*[1-\alpha/\text{number of overall hypothesis tests for non-inferiority to perform in STAGE II}]$ CI [Bonferonni adjustment to control for multiplicity]) of the difference of the means of the log10 transformed post-vaccination titer between Group j and Group 1 ($\alpha=2.5\%$ one sided). For each serotype, superiority will be demonstrated if the lower limit of the two sided adjusted 95% CI is greater than 1 (i.e., the log 10 of the difference should be above 0).

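### The Stage II confidence-level formula spends half the stated alpha: as printed it gives 99.375% or 98.75% intervals where Bonferroni on 2.5% one-sided needs 98.75% or 97.5%

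*SAP*

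**What the plan says.** For the Stage II primary tests, SAP 5.1.1.2 says "The non-inferiority tests will be performed using the paired t-test adjusted 95% 2 sided CI" and gives the level in brackets as 100*[1 - alpha/K], where K is the "total number of overall hypothesis tests to perform in STAGE II". The same sentence gives alpha as 2.5% one-sided. The two-sample tests of Group 2 against Group 1 use the same formula, and SAP 5.1.2.2.1 uses it again for Stage II superiority. SAP 5.5 states the design level as 2.5% one-sided with a Bonferroni adjustment in Stage II.

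K depends on Stage I. The within-Group 1 tests (1a and 1b) are always done. For the comparisons with Group 2, SAP 5.1.1.1 says that "only Group 1 and Group 2 that achieve non-inferiority at 28 days after last vaccination in STAGE I will continue to be tested". K is therefore 4 if Group 2 goes forward (1a, 1b, 2a, 2b, as the protocol synopsis lists them) and 2 if it does not. All four serotypes must pass within each overall test, so K counts overall tests and not serotypes.

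For Stage I non-inferiority, SAP 5.1.1.2 tests "using the two sample t-test 95% 2 sided CI of the difference of the means" and pairs this 95% level with the same 2.5% one-sided. No adjusted Stage II level is printed in the unredacted text.

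**The concern.** A two-sided interval at level 1 - c leaves c/2 in each tail. If alpha is one-sided, dividing alpha by K and subtracting from 1 halves the error a second time. The formula and the only alpha given for it therefore do not fit together.

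This is the decision rule for the Stage II primary non-inferiority tests, and it is reused for Stage II superiority. An analyst who programs the formula as printed uses a stricter interval than the stated alpha calls for. A second analyst who reads the label on the interval uses the ordinary Bonferroni level. Near the margin the two can reach opposite verdicts.

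**Working it through.** **Inputs from the documents.** Alpha is 2.5% one-sided (SAP 5.1.1.2, 5.5). K is 4 or 2 (SAP 5.1.1.1, protocol synopsis). The margin is 2-fold, 0.301 on log10 (SAP 5.1.1.1). There are 296 evaluable subjects per group (SAP Table 5.2). The protocol synopsis expects 60% to 70% to be eligible for the booster.

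**Reproducing the plan's own pairing.** For a one-sided test at level a, the matching two-sided level is 100*(1 - 2a). With a = 0.025 this is 95%, as the plan has it. The printed formula with K = 1 and alpha = 0.025 gives 100*(1 - 0.025) = 97.5%. It returns 95% only if alpha means 5% two-sided.

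**Levels.**

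| | K = 4 | K = 2 |
|---|---|---|
| Printed formula, alpha = 0.025 | 1 - 0.025/4 = 99.375% | 1 - 0.025/2 = 98.75% |
| One-sided per test | 0.3125% | 0.625% |
| One-sided sum | 4 x 0.3125% = 1.25% | 2 x 0.625% = 1.25% |
| Bonferroni on 2.5% one-sided | 1 - 0.05/4 = 98.75% | 1 - 0.05/2 = 97.5% |
| One-sided per test | 0.625% | 1.25% |
| One-sided sum | 2.5% | 2.5% |
| Critical z, printed / Bonferroni | 2.734 / 2.498 = 1.095 | 2.498 / 2.241 = 1.114 |

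The last row is the ratio of interval widths in large samples. The t-test ratio at these sizes is slightly larger (88 df, K = 4: 2.802/2.550 = 1.099). Note that 98.75% is the printed-formula level for two tests and also the Bonferroni level for four, so a report showing 98.75% would not reveal which rule was used.

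**Which level did the sponsor plan with?** The Stage II power tables are redacted, but Stage I can be checked. The SAP Stage I powers use 2.5% one-sided, because SAP 5.7 removed the Bonferroni adjustment. The protocol's Stage I powers keep Bonferroni over two tests. I assumed four equal, independent serotypes and a normal approximation. The noncentrality is then z(SAP power^(1/4)) + 1.960, and the predicted protocol power is the fourth power of Phi(noncentrality - critical z).

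- At 1.25% one-sided (ordinary Bonferroni), all ten protocol powers are matched within 2.0 points. The largest gap is 72.55 predicted against 74.52 printed.
- At 0.625% one-sided (the printed formula with K = 2), all ten are missed, by 1.4 points (97.52 against 98.9) to 15.5 points (47.66 against 63.12).

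**Possible power loss in the paired tests (1a, 1b).** Subgroup size is 296/2 = 148; 148 x 0.6 is about 89 and 148 x 0.7 is about 103. Assumed: true GMTR 1, independent serotypes with all four required, and a range of SDs for the log10 difference. Noncentral-t power to the fourth, Bonferroni level to printed level:

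| SD | K = 4, n 89 | K = 4, n 103 | K = 2, n 89 | K = 2, n 103 |
|---|---|---|---|---|
| 0.5 | 99.6 to 99.1% | 99.9 to 99.8% | 99.8 to 99.6% | above 99.9% for both |
| 0.6 | 93.8 to 88.9% | 97.6 to 95.4% | 97.0 to 93.8% | 98.9 to 97.6% |
| 0.7 | 75.3 to 63.2% | 86.4 to 77.9% | 85.1 to 75.3% | 92.5 to 86.4% |

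**Where the verdict changes.** A serotype passes when its observed GMTR exceeds 0.5 x 10^(t x SD/sqrt(n)). Take n = 89, SD 0.6, K = 4, so SD/sqrt(n) = 0.0636. The limit is 0.5 x 10^(2.550 x 0.0636) = 0.726 at the Bonferroni level and 0.5 x 10^(2.802 x 0.0636) = 0.754 at the printed level. An observed value between the two passes one rule and fails the other.

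**The case against.** The strongest reply is that the intent is plain. The interval is labelled an adjusted 95% two-sided interval, which the formula returns at K = 1 only with alpha = 5% two-sided. SAP 5.5 states 2.5% one-sided with Bonferroni in Stage II, and spending only 1.25% contradicts that. The Stage I power check points the same way. All of this stands. A reader might infer that the plan offers two equally supported readings, and the documents do not bear that out. They show that the printed formula is the error; they do not correct it.

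A second reply is that the literal rule is valid, only stricter. That is also true. A reader might infer that a multiplicity error threatens false positive claims, but the literal reading spends half the stated alpha, so the Stage II type I error is not inflated.

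Third, Stage II Table 5.3 and one assumption line in SAP 5.5 are redacted, as is protocol Table 12.2, so an adjusted level may stand there. That limits any statement that the level is nowhere given. It does not alter the mismatch in the visible formula.

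Finally, a reader might infer a large power loss for the Group 2 comparisons. The visible text gives neither a Stage II SD nor an assumed true ratio for them, so no figure is offered here.

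**Conclusion.** The formula is wrong as written: a conservative notation error with a recoverable intent. The levels are exact arithmetic. The printed formula gives 99.375% (four tests) or 98.75% (two), against the 98.75% or 97.5% that the stated alpha requires. Intervals are about 9.5% or 11.4% wider than needed in large samples.

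The cost in power is not known. For the paired tests at a true GMTR of 1 with 89 to 103 subjects, it is at most about 0.5 points if the SD of the difference is 0.5 or less. At SD 0.7 it is 8.5 to 12 points with four tests and about 6 to 10 with two. These figures rest on assumed SDs, on independent serotypes and on boosted subjects in both countries. SAP 5.1.3.1 restricts several post-booster analyses to Colombia, so the subgroups may be smaller.

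It is worth correcting because it sits in a primary decision rule and one line puts it right. Two pieces of Stage I wording need tidying at the same time, though neither is part of the main defect:

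- **Non-inferiority (SAP 5.1.1.2).** The rule still says "non-inferiority will be demonstrated if the lower limit of the two sided adjusted 95% CI is greater than 1/2", although SAP 5.7 removed that adjustment.
- **Superiority.** SAP 5.1.2.1 says "A Bonferonni alpha adjustment will be used to control for multiplicity". SAP 5.1.2.2.1 then says "The superiority tests will be performed using the two sample t-test 95% 2 sided CI of the difference of the means", with no adjustment, but decides that "superiority will be demonstrated if the lower limit of the two sided adjusted 95% CI is greater than 1". Whether 97.5% or 95% applies is not stated, a difference of 2.241/1.960 = 1.144 in width.

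**What to change.** In the Stage II parts of SAP 5.1.1.2 and 5.1.2.2.1, write the level as 100*[1 - 2*alpha/K]% two-sided with alpha = 2.5% one-sided, or define alpha as 5% two-sided and keep the formula. Print the results: 98.75% if four Stage II tests are performed, 97.5% if two.

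In the Stage I non-inferiority rule, delete the leftover word *adjusted*. For Stage I superiority, reconcile SAP 5.1.2.1 with 5.1.2.2.1 and print the level: 97.5% if Bonferroni over the two time points stays, 95% if it was dropped.

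The cost is SAP wording only. Against the literal text, the Stage II change relaxes the one-sided criterion per test from 0.3125% to 0.625% (four tests) or from 0.625% to 1.25% (two). It should therefore be recorded as a dated correction, with its reason, before any post-booster titers are unblinded. SAP 5.4 plans for the trial statistician to break the blind for the first analysis. It is written prospectively, so it does not show that this has happened, but it is a reason to make the correction early. The Stage II one-sided sum is then 2.5% for either K, and the Stage I non-inferiority level stays at 95%.

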5.1.2 Hypotheses and Statistical Methods for Secondary Objectives

5.1.2.1 Hypotheses

If the hypothesis for non-inferiority is demonstrated for the primary objective, then superiority hypotheses will be performed.

STAGE I

Individual Hypotheses for Each Serotype:

A superiority testing approach will be performed for each serotype to show the superiority of 2 doses of CYD dengue vaccine (28 days after last injection) compared to 3 doses of CYD dengue vaccine, in subjects seropositive at baseline. A superiority testing approach will also be performed for each serotype to show the superiority of 2 doses of CYD dengue vaccine (1 year after last injection) compared to the 3 doses of CYD dengue vaccine, in subjects seropositive at baseline.

A Bonferonni alpha adjustment will be used to control for multiplicity.

Individual hypotheses for each serotype will be as follows:

$$H_0^{ij}: GMT_{Group\ j}^i / GMT_{Group\ 1}^i \leq 1$$

$$H_1^{ij}: GMT_{Group\ j}^i / GMT_{Group\ 1}^i > 1$$

Where:

i=1, 2, 3, and 4 (each serotype),

j=2

The overall superiority of Group 2 to Group 1 at 28 days after last injection will be demonstrated if all 4 individual serotype null hypotheses are rejected. The same, overall superiority of Group 2 to Group 1 at 1 year after last injection will be demonstrated if all 4 individual serotype null hypotheses are rejected.

STAGE II:

Individual Hypotheses for Each Serotype:

Paired Test (Within Group 1)

A superiority testing approach will be performed for each serotype to show the superiority of a CYD dengue vaccine booster dose (28 days after booster) either 1 year and/or 2 years after last injection compared to the third CYD dose (28 days after third vaccination), i.e., within Group 1 comparisons, in subjects seropositive at baseline. A Bonferonni alpha adjustment will be used to control for multiplicity.

Individual hypotheses for each serotype will be as follows:

$$H_0^{ij}: GM(V_{Booster\ j}^i / V_{PD3\ j}^i) \leq 1$$

$$H_1^{ij}: GM(V_{Booster\ j}^i / V_{PD3\ j}^i) > 1$$

Where:

i=1, 2, 3, and 4 (each serotype),

j=1a or 1b (sub-group)

The overall superiority of Group j (j=1a or 1b) at 28 days after booster injection to Group j (j=1a or 1b) at 28 days after last 3rd-injection will be demonstrated if all 4 individual serotype null hypotheses are rejected.

Two Sample Test (Between Group 1 and Group 2)

A superiority testing approach will be performed for each serotype to show the superiority of a CYD dengue vaccine booster dose (28 days after booster) either 1 year and/or 2 years after a 2 dose schedule compared to the third CYD dengue vaccine (28 days after third vaccination), i.e., between Group 1 and Group 2 comparisons, in subjects seropositive at baseline. A Bonferonni alpha adjustment will be used to control for multiplicity.

Individual hypotheses for each serotype will be as follows:

$$H_0^{ij}: GMT_{Group j}^i / GMT_{Group 1}^i \leq 1$$

$$H_1^{ij}: GMT_{Group j}^i / GMT_{Group 1}^i > 1$$

Where:

i=1, 2, 3, and 4 (each serotype),

j=2a or 2b

The overall superiority of Group j (j=2a or 2b) to Group 1 at 28 days after booster injection will be demonstrated if all 4 individual serotype null hypotheses are rejected.

5.1.2.2 Statistical Methods

5.1.2.2.1 Statistical Methods for Hypotheses Objectives

STAGE I:

The superiority tests will be performed using the two sample t-test 95% 2 sided CI of the difference of the means of the log10 transformed post-vaccination titer between Group 2 and Group 1 ($\alpha=2.5\%$ one sided) at 28 days and 1 year after last injection. For each serotype, superiority will be demonstrated if the lower limit of the two sided adjusted 95% CI is greater than 1 (i.e., the log 10 of the difference should be above 0).

STAGE II:

Paired Test (Within Group 1)

The superiority tests will be performed using the paired t-test adjusted 95% 2 sided CI ($100*[1-\alpha/\text{total number of overall hypothesis tests for non-inferiority to perform in STAGE II}]$ CI [Bonferonni adjustment to control for multiplicity]) of the difference of the means of the log10 transformed post-vaccination titer between booster j and post Dose 3 j ($\alpha=2.5\%$ one sided). For each serotype, superiority will be demonstrated if the lower limit of the two sided adjusted 95% CI is greater than 1 (i.e., the log 10 of the difference should be above 0). Subjects with non-missing post dose 3 and post-booster titer will be included in this analysis.

Two Sample Test (Between Group 1)

The superiority tests will be performed using the two sample t-test adjusted 95% 2 sided CI ($100*[1-\alpha/\text{number of overall hypothesis tests for non-inferiority to perform in STAGE II}]$ CI [Bonferonni adjustment to control for multiplicity]) of the difference of the means of the log10 transformed post-vaccination titer between Group j and Group 1 ($\alpha=2.5\%$ one sided). For each serotype, superiority will be demonstrated if the lower limit of the two sided adjusted 95% CI is greater than 1 (i.e., the log 10 of the difference should be above 0).

5.1.2.2.2 Statistical Methods for Other Objectives

5.1.2.2.2.1 Immunogenicity

STAGE I:

In addition, immunogenicity will be assessed using the following parameters:

- Geometric means of the individual titer ratios (GMTR) for each serotype (parental strains) by baseline serostatus (1 year post-Dose 3 /28 days post-Dose 3)
- Group 1 only, GMTR for each serotype (parental strains) by baseline serostatus (28 days post-Dose 3 /post-Dose 2)

STAGE II:

- Seroconversion rates 28 days after the booster for each serotype (parental strains) of CYD dengue vaccine

5.1.2.2.2.2 Safety

STAGES I AND II:

Safety profile will be described after each injection for primary schedules and for booster dose.

The safety analysis will address the number and percentage of subjects with injection site reactions (pain, erythema, and swelling) from D0 and D07, solicited systemic reactions (fever, headache, malaise, myalgia, and asthenia) from D0 to D14, unsolicited AEs until D28, non-serious AESIs from D0 to D07, and unsolicited immediate systemic event occurring within 30 minutes after each injection. Solicited injection site reactions or solicited systemic reactions will be described according to time of onset, number of days of occurrence, action taken, and intensity.

Unsolicited AEs or non-serious AESIs will be described according to nature (MedDRA preferred term), time to onset, duration, intensity, action taken, and relationship to vaccination.

Unsolicited immediate systemic events will be described according to nature (MedDRA preferred term) and relationship to vaccination.

The number and percentage of subjects with SAEs, including serious AESIs will be described according to nature (MedDRA preferred term), seriousness criteria, outcome, and relationship to vaccination throughout the trial.

All AEs leading to study termination will be described according to nature (MedDRA preferred term) and relationship to vaccination.

Detection of symptomatic dengue cases

The number and percentage of subjects with a hospitalized VCD cases occurring during the trial after the injection will be described using safety analysis set.

